6. SUBJECT POPULATION

6.1. Type and Number of Subjects

Approximately 1150 subjects with mild to moderate AD who are on stable donepezil therapy will be enrolled.

In order to manage the total study enrollment, Axovant Sciences may suspend screening and/or enrollment at any site or study-wide at any time.

6.2. Inclusion Criteria

Subjects eligible for enrollment in the study must meet all of the following criteria:

1. Male or female subject with a clinical diagnosis of AD in accordance with the recommendations from the National Institute on Aging-Alzheimer's Association workgroups on diagnostic guidelines for AD (McKhann et al, 2011).
2. Subject has a documented history of at least 4 months of ongoing donepezil therapy for AD, with stable dosing of 5 or 10 mg/day for at least the last 2 months and with no intent to change for the duration of the study.
3. Subject has an MMSE score 12 to 24 inclusive at Screening and a Baseline MMSE score 10 to 26 inclusive. The difference between the Screening and Baseline MMSE score is less than or equal to 3 points. If a greater than 3-point difference between the Screening and Baseline MMSE score is in the opinion of the investigator due to recent changes in AD medication, the Run-In period may be extended for an additional 3 weeks after discussion with the Medical Monitor, during which time MMSE stability, defined as less than or equal to 3-point change over 3 weeks, must be observed.
4. Subject has a Hachinski Ischaemia score less than or equal to 4 at Screening.
5. Magnetic resonance imaging (MRI) or computed tomography (CT) scan performed within 12 months before screening with findings consistent with the diagnosis of dementia due to AD without any other clinically significant pathologies. If an MRI (preferred) or CT scan is unavailable or was performed longer than 12 months prior to Screening, one must be performed during the Screening Period (prior to Run-In).
6. Age greater than or equal to 50 years to less than or equal to 85 years at the time of Screening.
7. If female, subject must be:
 - a. Of non-childbearing potential (i.e., any female who is post-menopausal [greater than 1 year without menstrual period in the absence of hormone replacement therapy]) or surgically sterile; or,
 - b. If pre-menopausal or menopausal for 1 year or less, must have a negative pregnancy test and must not be lactating at the Screening and Baseline Visits. Female subjects of

childbearing potential and who are sexually active are required to practice adequate methods of birth control. Female subjects for whom menopausal status is in doubt in the opinion of the investigator will be required to use an adequate form of birth control. Acceptable, adequate form of birth control is defined as consistent use of combined effective methods of contraception including at least 1 barrier method.

Male subjects who are sexually active will also be required to use an adequate form of birth control as described above.

8. Subject has the ability to comply with procedures for cognitive and other testing in the opinion of the investigator.
9. Subject must be able to ingest pills (in tablet form) whole.
10. Subject lives with (or has substantial periods of contact with) a regular caregiver who is willing to attend visits, oversee the subject's compliance with protocol-specified procedures and study medication, and report on subject's status, and who has substantial contact with the subject. If the caregiver does not cohabit with the subject, he/she ideally should have a minimum of 10 hours total and at least 3 days contact with the subject per week. Prior to randomization, study representatives will review eligibility of non-cohabitating caregivers. Every effort should be made to have the same caregiver throughout the study.
11. Subject has provided full written informed consent prior to the performance of any protocol-specified procedure; or if unable to provide informed consent due to cognitive status, subject has provided assent and a legally acceptable representative has provided full written informed consent on behalf of the subject.
12. Caregiver has provided full written informed consent on his/her own behalf prior to the performance of any protocol-specified procedure.
13. General health status is acceptable for participation in a 24-week study.

6.3. Exclusion Criteria

A subject will not be eligible for inclusion in this study if any of the following criteria apply:

Other Causes for Dementia

1. Diagnosis of possible, probable, or definite vascular dementia in accordance with National Institute of Neurological Disorders and Stroke-Association Internationale pour la Recherche l'Enseignement en Neurosciences criteria.
2. History and/or evidence (including CT or MRI scan performed within the past 12 months or at Screening) of any other CNS disorder that could be interpreted as a cause of dementia (in the opinion of the investigator), e.g., cerebrovascular disease (transient ischemic attack, stroke, hemorrhage); structural or developmental abnormality; epilepsy; infectious, degenerative, or inflammatory/demyelinating CNS conditions; or Parkinson's disease.

3. Evidence of the following disorders where this is thought to be the cause of, or to contribute to the severity of, the subject's dementia: current vitamin B₁₂ deficiency, hypothyroidism, neurosyphilis, or Wernicke's encephalopathy.
4. Focal findings on the neurological exam (excluding changes attributable to peripheral injury) that are inconsistent with a primary diagnosis of AD.
5. History of existing negative amyloid positron emission tomography scan or similar brain amyloid imaging, or Screen Failure from research trial due to negative amyloid imaging within 5 years. Note: amyloid scan is not required for participation in this study.
6. Atypical clinical features or clinical course of dementia that would lead the investigator to conclude symptoms are more likely due to an alternate dementia diagnosis including, but not limited to, frontotemporal dementia, Lewy body dementia, or others.

Confounding Medical Conditions

7. History of significant psychiatric illness such as schizophrenia or bipolar affective disorder or any other significant psychiatric illness that in the opinion of the investigator would interfere with participation in the study; history of major depressive disorder in the past year, or current major depressive episode.
8. Significant suicide risk as defined by (1) suicidal ideation as endorsed on items 4 or 5 on the C-SSRS within the past year, at Screening or at Baseline, or; (2) suicidal behaviors within the past year, or; (3) clinical assessment of significant suicidal risk during subject interview.
9. Current psychosis that in the opinion of the investigator would interfere with the subject's ability to participate in this study.
10. History of epilepsy or unexplained seizure in the past 5 years, unexplained recent loss of consciousness, or history of significant head trauma with loss of consciousness.
11. History of malignancy during the 5 years before Screening. History of basal cell carcinoma and melanoma in situ are permitted. History of other cancers currently in a non-active state may be acceptable after review with the Medical Monitor.
12. Any clinically relevant concomitant disease including progressive liver or kidney dysfunction, history of myocardial infarction or unstable angina within 6 months of Screening, history of more than 1 myocardial infarction within 5 years of Screening, history of clinically significant stroke, or any other medical or psychiatric condition, which, in the opinion of the investigator, makes the subject unsuitable for inclusion in the study.
13. History of alcohol use disorder or other substance abuse disorder (excluding tobacco use), according to the Diagnostic and Statistical Manual of Mental Disorders, 5th Edition, criteria in the past 10 years.
14. History of Down syndrome or Intellectual Development Disorder.

Concomitant Medications

15. Participation in another investigational drug or device study in AD during the 60 days prior to the Screening Visit (Visit 1), or within 5 half-lives of use of the investigational drug prior

to the Screening Visit, whichever is longer. In addition, subjects who were previously screened for another study in AD but failed the entry criteria for that study may be screened with no time delay prior to the Screening Visit, provided that, in the opinion of the investigator, and after review with the Medical Monitor, there is a realistic possibility that the subject would be eligible. However, Screen Failures due to negative amyloid imaging within 5 years will not be eligible for enrollment (see exclusion criterion 5).

16. Treatment with any concomitant medications as detailed in [Table 1](#). Memantine and other treatments for dementia including AChEIs other than donepezil must have been discontinued 30 days prior to entry into the Single-Blind Run-In Period. Other prohibited medications as outlined in [Table 1](#), unless otherwise specified, need to have been discontinued for 5 half-lives prior to screening and assessed as no longer clinically necessary for the subject. Subjects taking memantine or other agents to treat cognitive impairment associated with AD at the time of Screening will be considered Screen Failures. However, subjects with recent discontinuation prior to Screening of memantine or other agents to treat cognitive impairment who will have been discontinued for 30 days prior to the Single-Blind Run-In Period may continue. Subjects who screen fail may be rescreened once (see [Section 6.5](#)).

Unacceptable Test/Laboratory Values

17. Postural hypotension (fall in systolic blood pressure of greater than 30 mmHg or fall in diastolic blood pressure of greater than 20 mmHg on standing compared to sitting) at the time of screening. Subjects who present at the time of screening with postural hypotension yet have no known history of postural hypotension, nor underlying medical condition related to hypotension, may be rescreened.
18. Persistent or recurrent liver enzyme elevations, alanine transaminase (ALT) and/or aspartate aminotransferase (AST) greater than or equal to 2.0 times upper limit of normal (ULN).
19. Total bilirubin over 1.5 x ULN except due to documented Gilbert's disease.
20. Calculated creatinine clearance less than 40 mL/min (Cockcroft-Gault formula) at Screening:

Adult males: $[(140 - \text{age in years}) \times (\text{weight in kg})] \div 72 \times \text{serum creatinine}^*$

Adult females: $0.85 \times [((140 - \text{age in years}) \times (\text{weight in kg})) \div 72 \times \text{serum creatinine}^*]$

* in mg/dL

21. Positive hepatitis B surface antigen or hepatitis C antibody test.
22. Confirmed corrected QT interval (QTc) value greater than or equal to 450 msec for males or greater than or equal to 470 msec for females. Subjects with a QRS value greater than 120 msec and subjects with a QTc value less than 500 msec may be eligible following discussion with the Medical Monitor.

Other

23. Previous exposure to RVT-101 or SB742457.
24. Subject is unable to take study medication as prescribed throughout the study (with assistance is acceptable), has a significant history of non-compliance with prescribed medication, or is at risk of non-compliance with study medication or procedures.
25. Subject or caregiver is an immediate family member or employee of the participating investigator, any of the participating site staff, or of the sponsor study staff.
26. Subject was prescribed cognitive tasks for cognitive rehabilitation performed under medical supervision in the 3 months prior to Screening or plans to participate in cognitive rehabilitation during the study.
27. Subject has participated in a program of neurostimulation in the past 3 months or plans to participate in a program of neurostimulation during the course of the study.

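### The Cockcroft-Gault expression printed in exclusion 20 leaves its denominator unbracketed; worked left to right it multiplies by serum creatinine, which contradicts the named formula and a lower limit on clearance

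*Protocol*

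**What the plan says.** Protocol Section 6.3, criterion 20, stands under the sub-heading for unacceptable test or laboratory values and excludes a subject with "Calculated creatinine clearance less than 40 mL/min (Cockcroft-Gault formula) at Screening". Two lines follow:

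- Men: the product of (140 − age) and weight in kg, in square brackets, then ÷ 72 × serum creatinine.
- Women: 0.85 times a bracketed expression of the same structure.

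A footnote gives creatinine in mg/dL. In neither line does a bracket group 72 with serum creatinine. The formula appears nowhere else in the protocol or in the SAP addendum, and there is no worked example.

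The only other criterion that mentions the kidney is exclusion 12, "Any clinically relevant concomitant disease including progressive liver or kidney dysfunction", which depends on the investigator's opinion and sets no number.

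Table 3 lists creatinine as a clinical chemistry parameter but does not list creatinine clearance. Weight is recorded separately as a vital sign (Section 8.3.2.4). The documents do not say whether the laboratory, the eCRF or the site combines the two.

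**The concern.** Division and multiplication have equal rank, so the printed string evaluated from left to right puts serum creatinine in the numerator. The result then increases as creatinine increases. That does not fit the formula the criterion names, and it does not fit a rule that excludes low clearance.

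This is a working eligibility rule, and the only numeric renal limit in the protocol. Whoever needs the calculation has one printed source for it. About 185 centers are planned, and Section 8 allows no waivers except for immediate safety concerns. A site worksheet or an edit check coded from the string as it stands would admit some subjects whom the criterion is meant to keep out and reject some whom it is meant to let in. The renal profile of the Safety Population would then differ from the one the criterion describes.

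**Working it through.** The documents state no calculated clearance, so there is no figure to reproduce. The check is to evaluate the expression under both readings.

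**Inputs from the protocol:** the constants 140, 72 and 0.85; creatinine in mg/dL; exclusion below 40 mL/min; and the age range, "Age greater than or equal to 50 years to less than or equal to 85 years at the time of Screening".

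**Assumed inputs:** weights of 50 to 80 kg and the individual creatinine values. The documents give neither, so these profiles are illustrations.

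**Formulae.** Let k = (140 − age) × weight ÷ 72, multiplied by 0.85 for women, and let Cr be serum creatinine.

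- Division, with denominator (72 × Cr): clearance = k ÷ Cr. Excluded when Cr is above k ÷ 40.
- Literal left to right: result = k × Cr. Excluded when Cr is below 40 ÷ k.

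The two computed values coincide only at Cr = 1.0. The two eligibility decisions agree over a whole band between 40 ÷ k and k ÷ 40. If k is above 40, both readings admit inside the band; if k is below 40, both exclude. Below the band, division admits and the literal reading excludes. Above it, division excludes and the literal reading admits.

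**Man, 75 years, 75 kg.** k = 65 × 75 ÷ 72 = 67.7. Limits: 40 ÷ 67.7 = 0.59 and 67.7 ÷ 40 = 1.69. Both readings admit him from 0.59 to 1.69 mg/dL. At 2.0: 67.7 ÷ 2.0 = 33.9 (excluded) against 67.7 × 2.0 = 135.4 (admitted).

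**Woman, 85 years, 50 kg.** k = 0.85 × 55 × 50 ÷ 72 = 32.5. Limits: 32.5 ÷ 40 = 0.81 and 40 ÷ 32.5 = 1.23. Both readings exclude her from 0.81 to 1.23 mg/dL. At 0.7: 46.4 (admitted) against 22.7 (excluded). At 1.4: 23.2 (excluded) against 45.5 (admitted).

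**Range over assumed profiles:**

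| Profile | k | Band where decisions agree (mg/dL) | Decision in band | Example of a flip (division / literal, mL/min) |
|---|---|---|---|---|
| Woman, 85 y, 50 kg | 32.5 | 0.81 to 1.23 | excluded | Cr 1.4: 23.2 / 45.5 |
| Woman, 75 y, 60 kg | 46.0 | 0.87 to 1.15 | admitted | Cr 0.8: 57.6 / 36.8; Cr 1.5: 30.7 / 69.1 |
| Man, 75 y, 75 kg | 67.7 | 0.59 to 1.69 | admitted | Cr 2.0: 33.9 / 135.4 |
| Man, 60 y, 80 kg | 88.9 | 0.45 to 2.22 | admitted | Cr 3.0: 29.6 / 266.7 |
| Man, 50 y, 80 kg | 100.0 | 0.40 to 2.50 | admitted | Cr 3.0: 33.3 / 300.0 |

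The band is narrowest where k is near 40, which in these examples means the older and lighter women. It is wide for the younger and heavier men.

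**The case against.** The strongest reply is that the intended rule is not in doubt. The criterion names Cockcroft-Gault and calls the result a clearance, and an inline ÷ 72 × creatinine is often meant as division by the product. Only that reading suits a lower limit, and an experienced reader would supply the missing bracket. This stands: the defect is one of notation, and the intent can be recovered from the criterion itself.

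A reader might go further and infer that the cut-off works in reverse in this trial, admitting impaired kidneys and excluding healthy ones. The documents do not support that. No section says that sites calculate by hand or that the printed string was programmed. Serum creatinine is measured at Screening, and the laboratory gives sites its reference ranges, so a creatinine of 2.0 mg/dL beside a clearance of 135 might well be noticed. Even under literal use, healthy subjects are not excluded as a class: the assumed man of 60 years and 80 kg is admitted under both readings at every creatinine from 0.45 to 2.22 mg/dL.

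Exclusion 12 is a partial safeguard. It could catch some subjects wrongly passed by criterion 20, but it depends on opinion and would not bring back anyone wrongly excluded.

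Finally, the bracket could have been lost when the PDF was converted to text. That is unlikely, because the other brackets survive in both lines and the female line's outer bracket closes after creatinine without grouping the denominator. It is not excluded: a stacked or grouped denominator could have been flattened in the same way twice. The typeset page settles this.

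**Conclusion.** The point holds as a notation error in an operative eligibility rule. As it appears in the text, the expression does not match the formula it names or the purpose of the limit it serves. The effect on any one subject, if the expression was used literally, can be large: 33.9 against 135.4 mL/min for the assumed man of 75 years and 75 kg at 2.0 mg/dL. It would change eligibility only outside the agreement band.

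How many subjects this touches, if any, cannot be estimated. The documents give no distribution of weight or creatinine and do not say how clearance was calculated. The illustrations rest on assumed weights and creatinine values. Sample size, power, alpha and the endpoints are not affected, and nothing here questions the 40 mL/min threshold. This is a small correction, worth making because it concerns safety and costs almost nothing.

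**What to change.** Print the denominator as (72 × serum creatinine) in both lines, so that the male line is [(140 − age) × weight] ÷ (72 × serum creatinine) and the female line is 0.85 times the same. Keep the 40 mL/min cut-off as it is.

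Then confirm in writing which calculation the laboratory, the eCRF or the sites actually used. If it was division, record that and close the point. If any of them multiplied, recompute clearance from screening age, weight, sex and creatinine for randomised subjects and for those screen-failed on criterion 20, where the data are available, and list the decisions that change.

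The SAP addendum expects the trial to conclude in late September 2017. By that stage a corrected line could no longer alter who was randomised, and the check of the calculation is the part that keeps its value. The cost is one bracket pair per line in an amendment or clarification letter, plus one query on the calculation. Recomputation is needed only if that query shows literal use.

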6.4. Other Eligibility Criteria Considerations

To assess any potential impact on subject eligibility with regard to safety, the investigator must refer to the following document(s) for detailed information regarding warnings, precautions, contraindications, AEs, and other significant data pertaining to the investigational product(s) being used in this study:

- RVT-101 Investigator's Brochure
- Package insert/label for donepezil hydrochloride.

6.5. Screening Failures

Screen Failures are defined as subjects who sign an informed consent form (ICF) for RVT-101-3001 but are never subsequently randomized and who do not enter the Single-Blind Run-In Phase. A minimal set of screen failure information is required including demography, screen failure details, eligibility criteria, and any serious adverse events (SAEs).

Subjects who are Screen Failures may be rescreened once only after approval by the study Medical Monitor.

6.6. Withdrawal Criteria

6.6.1. Reasons for Withdrawal

A withdrawal from the study is defined as withdrawing any time after entering the Single-Blind Run-In Phase and before completion of the Week 24 Visit (Visit 8). Subjects who permanently discontinue use of investigational product will be considered to be withdrawn from the study. Subjects may withdraw from the study at any time and for any reason. The investigator (or designee) must document the reason for withdrawal in the appropriate section of the electronic case report form (eCRF). Information related to AEs will continue to be collected as per usual

procedures on subjects who have discontinued investigational product. Withdrawn subjects will not be replaced. The reasons for subject withdrawal will be recorded and may include, but are not limited to:

- Any clinical AE, laboratory abnormality, or other medical condition or situation occurs such that continued participation in the study would not be in the best interest of the subject in the opinion of the investigator
- Pregnancy of female subject (discontinuation of treatment, but will be followed until the outcome of pregnancy is known)
- Significant protocol violation
- Subject requests to discontinue for any reason; it is important to determine whether the withdrawal of consent is primarily due to an AE, lack of efficacy, or other reason

The above reasons do not automatically lead to withdrawal from the study in all cases. The final decision will be based on consultation between the principal investigator and the study Medical Monitor, with the ultimate decision by the principal investigator or subject. Subjects may discontinue from treatment with study investigational product but may agree to continue to be followed for additional safety evaluation.

If a subject meets discontinuation criteria during treatment, an Early Termination Visit will be required (Section 6.6.2).

6.6.2. Subject Withdrawal Procedures

If a subject is prematurely discontinued from treatment with the investigational product, the investigator must make every effort to perform the evaluations scheduled for the Early Termination Visit (Table 2). In the case where the subject permanently discontinues study medication between scheduled clinic visits, he/she should be recalled to the clinic as soon as possible and preferably within 7 days of stopping study medication for the Early Termination Visit.

Lost to follow-up: If a subject is lost to follow-up, every effort must be made by study center personnel to contact the subject, inquire about the reason for discontinuation/withdrawal, and follow up with any unresolved AEs/SAEs. A minimum of 3 attempts at contact should be made with 1 contact being by certified letter. All measures taken to contact the subject and information received during those attempts must be documented.

7. STUDY TREATMENT

7.1. Investigational Product and Other Study Treatment

Investigational product in this study is defined as RVT-101 tablets and its matching placebo, and will be provided by Axovant Sciences. RVT-101 and placebo tablets will be indistinguishable from each other.

Investigational product for the Single-Blind Run-In Period (Weeks -3 to 0) will be supplied as single individual bottles, each bottle containing 50 tablets which is sufficient medication for 3 weeks plus 29 days overage. Investigational product for the Double-Blind Treatment Period (Weeks 0 to 24) will be supplied at Visits 3, 5, 6, and 7 as a single individual bottle containing 50 tablets, which is sufficient for 6 weeks plus 8 days overage. A new bottle of investigational product will be dispensed at each visit *except* at Visit 4, where no drug is dispensed. In the event that the Single-Blind Run-In period is extended to repeat the MMSE, no new investigational product will be dispensed. Drug accountability will be checked, and subjects will be redispensed the study medication bottles they received at Visit 2.

Subjects enrolled in this study will have been on donepezil for at least 4 months and on a stable dose of 5 or 10 mg/day for at least 2 months prior to enrollment and will continue this regimen unchanged for the duration of the study. Axovant Sciences will supply donepezil tablets in this study at the stable clinical dose for each subject. Study-dispensed donepezil will start in the Single-Blind Run-In Period. Subjects should be clearly instructed to take only study-dispensed donepezil during the duration of this study until V8, and to discontinue their clinical supply of donepezil provided by their personal physician. Subjects should be instructed to take their study-supplied donepezil exactly as they had been taking their clinically prescribed donepezil during the previous 2 months, including at the same time of day. Compliance with study-dispensed donepezil should be assessed at each visit. Confirmation of discontinuation of clinically supplied donepezil from subject and caregiver should be obtained at Visit 4 (Week 3) and re-confirmed thereafter as needed. Subjects will need to re-start their clinical supply of donepezil (clinically prescribed by the Investigator or treating physician) after V8; subjects not entering the open-label extension study RVT-101-3002 will remain at the same stable dose until V9.

Study-supplied donepezil will be supplied throughout the study as single individual bottles that contain 90 tablets. This is sufficient to cover all visit intervals plus windows as allowed by the protocol. A new bottle of donepezil will be dispensed according to the Time and Events Schedule in Table 2. In the event that the Single-Blind Run-In period is extended to repeat the MMSE subjects will be redispensed the medication they received at Visit 2.

Characteristic	Investigational Product	
Product name:	RVT-101	Placebo
Formulation description:	Pink film-coated round tablets	Pink film-coated round tablets
Dosage form:	35-mg tablet	Placebo tablet
Unit dose strength(s)/	35 mg	N/A
Dosage level(s):	(1 tablet per dose)	(1 tablet per dose)
Route of administration:	Oral	Oral
Duration (Run-in Period):	N/A	3 weeks
Duration (Treatment Period):	24 weeks	24 weeks
Dosing instructions:	Take 1 tablet orally each morning without regard to food	Take 1 tablet orally each morning without regard to food
Clinical Supplier	Catalent Pharma Solutions, Kansas City, MO USA	Catalent Pharma Solutions, Kansas City, MO USA

Characteristic	Study-Dispensed Donepezil	
Product name:	Donepezil hydrochloride (5 mg and 10 mg tablets)	
Formulation description:	5 mg tablets: white to off white film-coated, round tablets debossed with ML89 on one side 10 mg tablets: yellow film-coated round tablets debossed with ML88 on one side	
Dosage form:	Tablet	
Unit dose strength(s)/	5 mg (1 tablet per dose) and 10 mg (1 tablet per dose)	
Dosage level(s):		
Route of administration:	Oral	
Duration (Run-in Period):	3 weeks	
Duration (Treatment Period):	24 weeks	
Dosing instructions:	Take 1 tablet orally as prescribed	
Clinical Supplier	Catalent Pharma Solutions, Kansas City, MO USA	

